2.1.3.2 Secondary effectiveness endpoints (All procedures)

2.1.3.2.1 Surgeon assessment of robotic usability.

From the usability questionnaire (to surgeons) the response to the final question: "Indicate whether the device performance met your expectation in procedural success" will be used. Three responses are available, complete procedure success, partial procedural success, no procedural success.

Patients will be classified as:

Sponsor: MMI Product: Symani system for microsurgical anastomosis Study: PRIMO	
Statistical Analysis Plan Final 22 November 2024	

Success="yes" if the response is 'complete procedural success'

And success='No' otherwise. A sensitivity analysis will be performed with 'partial procedural success' included in success=Yes

Note, this endpoint will only be derived for the prospective subpopulation.

For this endpoint the patient is the unit for analysis.

2.1.3.2.2 Time for each anastomosis execution.

Robotic usage time and manual time are recorded for each procedure (free flap, replantation, lymphatic) and each anastomosis within a procedure within an operation on Dendrite's form R, and Castor's Anastomosis Data Form (procedure specific).

Total time will be derived (for each anastomosis) as robotic time + manual time.

For this endpoint, the anastomosis is the unit of analysis.

In addition to reporting the time per anastomosis, for each procedure the overall total robotic suturing time, the total manual suturing time and total suturing time will be derived as follows:

For each procedure within an operation, the total robotic usage time will be derived as the sum of the time recorded for each anastomosis within that procedure.

For each procedure within an operation, the total manual time will be derived as the sum of the time recorded for each anastomosis within that procedure.

For each procedure within an operation, the total suture time (robotic plus manual) will be derived as:

Total robotic time + total manual time within that procedure.

For this additional summary, the procedure is the unit of analysis.

2.1.3.2.3 Intraoperative need to redo the anastomosis (yes or no)

Castor' and Dendrite's anastomosis form has a question 'timing of anastomosis', with the options 'first attempt' and 'subsequent attempt'. Subsequent attempt is a redo form.

Redo forms will be 'aligned' with first attempt forms by matching anastomosis type (free flap, replantation) according to the form completed and with surgery type by matching the responses to the questions:

Side, vessel type and vessel diameter.

Sponsor: MMI Product: Symani system for microsurgical anastomosis Study: PRIMO	
Statistical Analysis Plan Final 22 November 2024	

For lymphatic surgery matching will be done using type (lymphatic anastomosis form completed), type of anastomosis and vein diameter.

Any anastomosis which has at least one redo form will be classified as redo="yes".

Any anastomosis which does not have a matching form for subsequent attempt will be classified as redo="No".

If there are subsequent attempt forms which do not directly align with a first attempt form, this will be resolved by clinical review so all subsequent attempt forms are aligned with a first attempt form.

For this analysis, the anastomosis is the unit of analysis.

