2.1.3.5.2 Intra-operative anastomosis patency

For each anastomosis, Dendrite form R or Castor Anastomosis Data Form asks the question 'Success of anastomosis'. If the response is 'Patent' then intraoperative patency = Yes.

If response = 'failed' or 're-done' then intraoperative patency = No.

Note, this endpoint will only be assessed using the index operation where the timing of anastomosis = 'First attempt'.

The unit of analysis is the anastomosis.

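### Intra-operative redo can be misclassified: an absent redo form always means 'No' despite a recorded 're-done' answer, and the keys linking redo forms to first attempts need not be unique

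*SAP*

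**What the plan says.** Intra-operative redo is a secondary endpoint for replantation, free flap and lymphatic surgery (protocol synopsis, Secondary Endpoints; SAP 1.3.1). SAP 2.1.3.2.3 derives it per anastomosis, from forms alone:

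- **Source.** Each anastomosis form states whether it is a first or a subsequent attempt: "Subsequent attempt is a redo form".
- **Key, flap and replantation.** The form type, plus "Side, vessel type and vessel diameter".
- **Key, lymphatic.** "For lymphatic surgery matching will be done using type (lymphatic anastomosis form completed), type of anastomosis and vein diameter".
- **Yes.** "Any anastomosis which has at least one redo form will be classified as" 'yes'.
- **No.** "Any anastomosis which does not have a matching form for subsequent attempt will be classified as" 'No'.
- **Safeguard.** "If there are subsequent attempt forms which do not directly align with a first attempt form, this will be resolved by clinical review".

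SAP 2.1.3.5.2 derives intra-operative patency from the item 'Success of anastomosis' on the same form: "If response = 'failed' or 're-done' then intraoperative patency = No". It restricts this to first attempts: "this endpoint will only be assessed using the index operation where the timing of anastomosis" is a first attempt.

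SAP section 2 (Figure 1) expects several procedures within a surgery type and several anastomoses within a procedure. SAP 2.4.4.2.3 analyses redo with Model 1/1a, which gives results by recipient site or location and by subpopulation.

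**The concern.** Two features of the rule can give a wrong label.

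**(a) No form means 'No'.** The rule has no missing category and does not consult the 're-done' answer. A first attempt recorded as re-done, but with no second form, counts as not patent in one table and as not redone in another. Every absent redo form becomes a 'No', so the reported rate falls and the table shows no missing values. SAP 2.5.6 expects a fair amount of missing data in the retrospective collection, although it does not mention redo forms.

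**(b) The key does not identify an anastomosis.** It contains no anastomosis or procedure number, and the lymphatic key has neither side nor location. Two accompanying veins of one flap with equal diameter, or two lymphatic anastomoses of the same type and vein diameter, share a key. The SAP does not say what happens when a redo form fits more than one first attempt.

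At stake are the reported redo rate, its breakdown by recipient site or location, and its consistency with patency.

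**Working it through.** The documents give no expected rate, sample size or power for intra-operative redo, so there is no figure of the plan's own to reproduce. The check is a comparison of sections followed by an illustration.

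**1. One anastomosis under both derivations.** Take a first attempt with 'Success of anastomosis' = 're-done' and no subsequent-attempt form.

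- Section 2.1.3.5.2: patency = No, because it was re-done.
- Section 2.1.3.2.3: redo = 'No', because no form matches.
- The review clause does not reach this case, because it is triggered by a subsequent-attempt form and there is none.

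Section 2.1.3.2.4 handles the parallel problem for post-operative redo: it has a fallback for a 'yes' answer without a re-operation form and ends in a missing category. Section 2.1.3.2.3 has neither. The general rule in 2.5.2, which excludes outcomes with insufficient information, never applies because 'No' has already been assigned.

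**2. Effect of absent forms.** Let q be the true redo rate and m the share of redos without a form. With no ties, the derived rate is q(1 − m). With q = 5% (assumed):

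- m = 10%: 5% × 0.90 = 4.5%, one tenth lower.
- m = 30%: 5% × 0.70 = 3.5%.

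**3. Effect of ties.** Assume k first attempts per patient, each falling independently into one of c equally likely key cells.

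- Chance that a redone anastomosis shares its key with another: 1 − (1 − 1/c)^(k−1).
- Derived rate if a tied form flags every candidate, with all forms present: 1 − (1 − q)(1 − q/c)^(k−1).

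With q = 5% and k = 3 (both assumed; SAP 1.7 says that the number of anastomoses per patient was unknown at design):

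| Key cells c | Chance of a tie | Derived rate, all candidates flagged |
|---|---|---|
| 3 | 1 − (2/3)² = 55.6% | 1 − 0.95 × 0.9833² = 8.1% |
| 5 | 1 − 0.8² = 36.0% | 1 − 0.95 × 0.99² = 6.9% |
| 8 | 1 − 0.875² = 23.4% | 1 − 0.95 × 0.99375² = 6.2% |
| 20 | 1 − 0.95² = 9.8% | 1 − 0.95 × 0.9975² = 5.5% |

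If a form that fits two first attempts is linked to only one, without further information, the choice is wrong half the time. Each error makes one false 'Yes' and one false 'No' in the same patient. The overall rate does not change, but a label can move between recipient sites or locations.

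**4. Both effects together.** Replace q by q(1 − m) in the tie formula. With q = 5%, k = 3, c = 4 and m = 30%, the derived rate is 1 − 0.965 × (1 − 0.035/4)² = 5.2%. That looks almost correct, yet 0.30 × (1 − 0.035/4)² = 29.5% of true redos are labelled 'No'. A plausible overall rate therefore does not show that the labels are right.

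**The case against.** **The SAP may intend a one-to-one link.** Its stated aim is that every subsequent-attempt form ends up aligned with a first attempt, in the singular. On that reading ties do not inflate the rate. This stands, and the inflation figures are therefore conditional. It does not say how a tie is settled, so individual labels can still be wrong.

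**Clinical review may cover ties.** A form that fits two candidates arguably does not align directly with either. That reading is possible, but the text does not state it: read literally, a tied form does align. Adding the words would settle it.

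**An absent redo form is an incomplete record.** SAP 2.1.3.1 expects a form for each anastomosis, so a 're-done' answer without a second form could be queried. That is true, and the two definitions agree when the records are complete. But the derivation contains no such cross-check, and SAP 1.1 makes retrospective collection depend on availability.

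**The illustration may be pessimistic.** The documents do not say how finely diameter is recorded, and the flap and replantation key also carries side and vessel type. With 20 cells the inflation is only half a percentage point. This also stands.

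A reader might infer that the rule inflates lymphatic rates and deflates retrospective rates, so that comparisons by surgery type and by subpopulation are distorted in opposite directions. The documents do not support this. They give no frequency of ties or absent forms in any group, and models are fitted separately by surgery type.

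**Conclusion.** The point holds in this form: under SAP 2.1.3.2.3, redo status can be misclassified. Part (a) is the firmer half, since it follows from the stated rule on any reading: a recorded 're-done' answer is ignored, missing is impossible, and the endpoint can contradict patency. Its size is proportional: 10% of redo forms absent lowers the rate by about one tenth. Part (b) is a missing tie rule. Its effect ranges from none on the overall rate (arbitrary one-to-one link, with wrong labels by site or location) to a derived 5.5% to 8.1% against a true 5% (every candidate flagged, 20 down to 3 cells, 3 anastomoses per patient). All these inputs are assumptions.

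It would go too far to say that redo status *is* misclassified in this study, because nothing in the documents shows how often either situation arises. The endpoint is secondary and has no benchmark or success criterion. The primary endpoint (SAP 2.1.3.1) does not use this link between forms. The change should be made, but the study's main conclusion does not depend on it.

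**What to change.** Amend SAP 2.1.3.2.3 as follows:

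1. Set redo = Yes if the first-attempt form answers 're-done', or if a subsequent-attempt form is assigned to it.
2. Assign each redo form to exactly one first attempt within the same procedure, using a 're-done' or 'failed' answer to help resolve ties.
3. Send non-unique matches, as well as non-matches, to the clinical review already planned.
4. Set redo to missing when there is no redo form and 'Success of anastomosis' is unanswered. Report the number missing by subpopulation, in line with SAP 2.4.1.

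Other details could work. The minimum is to cross-check the 're-done' answer and to review non-unique matches. The cost is SAP wording and derivation code, since the item is already on the anastomosis form. The downside is that a few more records go to review.

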2.1.3.2.4 Post-operative need to redo the anastomosis within 7 days (yes or no)

The need for a re-operation (yes/no) is recorded on several forms, namely Castor operation data forms contain the question 'Any post-operative need to redo?' and all post-surgery visit forms (visit 1 (24 hours), visit 2 (4 days post-surgery), visit 3 (14 days post-surgery) and visit 4 (30 days post-surgery for free flaps and replantations, 24 weeks post-surgery for lymphatic operations) and the unplanned visit form have the question "Postoperative need to redo?".

Note, the derivation of this endpoint is at the procedure level. Re-operation forms are by procedure (free flaps, replantation, lymphatic surgery) and will be 'aligned' to the index operation of the same type.

If, for that procedure, the answer to any of the questions above is yes, there should be a re-operation form for that procedure

The date of re-operation is recorded on the re-operation form.

The time (in days) to re-operation will be determined as:

Date of reoperation – date of index operation.

If the time to re-operation is ≤ 7 days then the patient will be classified as reoperation within 7 days = Yes.

If there are no re-operation forms where the time to re-operation is ≤ 7 days then the procedure will be classified as re-operation within 7 days = No.

If there are no re-operation forms (and ALL questions above are No, for need for a re-operation) for that procedure type, then re-operation within 7 days = No.

If any of the questions suggest there was a re-operation but there is no accompanying re-operation form then the following approach will be used.

- If the answer to re-operation needed is "yes" on the index operation form or the form for visit 1 (24 hours) or visit 2 (4 days) is Yes, then re-operation = Yes.

Sponsor: MMI Product: Symani system for microsurgical anastomosis Study: PRIMO	
Statistical Analysis Plan Final 22 November 2024	

- If the answer for re-operation on the unplanned visit form is “yes”, then if the date of the unplanned visit is within 7 days of the date of the index procedure, then re-operation = “yes”.
- If a clinical review of available data suggests there was a re-operation within 7 days then re-operation = “yes”.
- In other circumstances re-operation within 7 days will be missing.

This analysis is at the procedure level.

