2.1.3.3 Secondary Effectiveness Endpoints - Free Flap and Replantation

2.1.3.3.1 Ischemia time

Warm ischemia time is captured directly on the operation CRF (for free flaps and replantations).

2.1.3.3.2 Free flap failure or loss at discharge/replantation failure or loss (subsequent amputation).

This endpoint only refers to flap procedures or replantations.

The unit of analysis is the flap/replantation, i.e. at the procedure level.

Separate variables will be derived for flaps and replantations.

For each flap, Dendrite’s form H and Castor’s Free Flap Operation Visit operation visit: Operation Data Forms record the answer to the question ‘Flap survival at recipient site at discharge’, with options ‘100% - complete survival’, ‘partial survival’, ‘zero survival’, ‘buried flap’ or ‘unknown’. In Dendrite, the same form is used for replantations, so if the procedure is replantation, then the question will be interpreted as ‘Replantation survival at discharge’.

Each flap will be classified as ‘loss/failure’ = yes if the response to the question is ‘zero survival’ and loss/failure = ‘no’ if the response is ‘100% complete survival’ or ‘Partial survival’. If the response is ‘buried flap’ or ‘unknown’ the response will be missing.

For replantations the options are:

Yes, No, partial failure, not applicable

Sponsor: MMI Product: Symani system for microsurgical anastomosis Study: PRIMO	
Statistical Analysis Plan Final 22 November 2024	

Each replantation will be classified as ‘loss/failure’ = yes if the response to the question is ‘yes’ and loss/failure = ‘no’ if the response is No or ‘Partial failure’. If the response is not applicable the response will be missing.

For both variables, if the question is not answered the variable will be missing.

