2.1.5.1.3 All cause re-admission rates

Dendrite's Form U1, and Castor's Visit Forms (1-4), is used to collect follow-up information. If all forms have the response to the question 'Any unplanned re-admission'=No, then the patient will be classified as any re-admission within 30 days = no.

If any form has the response to the question 'Any unplanned re-admission to hospital' = Yes, the patient will be classified as 'yes' to any re-admission.

For each form reporting a re-admission, the time to re-admission (in days) will be derived as

Date of re-admission – date of index operation +1.

If there are multiple forms for the same patient where any re-admission = Yes, the time of the earliest re-admission will be used to determine the time to re-admission.

For patients with no re-admissions, time to re-admission will be determined as follows:

In Dendrite, date of follow-up is recorded on form U1 (a follow-up visit form), form U2 (the adverse event form, here it can be recorded twice, once for an AE and once for an adverse device effect) and on form U3 (protocol deviation form).

In Castor, data of follow-up is recorded on Visit Forms (1-4), Repeating Data: Adverse Events, and on Repeating Data: Protocol Deviation Form.

All forms (there may be multiple of each type of form) will be inspected. The latest date will be used to determine time to re-admission.

Time to re-admission (in days) will be calculated as latest follow-up date – date of index operation +1. The patient will be censored in analysis.

2.1.5.1.4 All cause re-operation rates up to 30 days.

Dendrite's Form H, and Castor's Free Flap Operation Visit: Operation Data Form, collects information on whether a donor site re-operation was required, and if so, the data and type of re-operation. In Dendrite, forms J, K, L, M, N and P ask whether a recipient site re-operation was needed (each form collects data for a different recipient site). Form Q collects information on the date and type of recipient site re-operation. In Castor, the repeating data forms: Breast, Head & Neck, Lower Limb, Perineum, Trunk, and Upper Limb Recipient Data ask whether a recipient site re-operation was needed (each form collects data for a different recipient site). The last two questions on each repeating data form for the recipient site collect information on the date and type of recipient site re-operation.

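### With no re-operation form, an undated 'Yes' on the index operation form counts as a redo within 7 days, so a later redo can enter the 7-day rate

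*SAP*

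**What the plan says.** SAP section 2.1.3.2.4 derives the 7-day redo endpoint for each procedure. The primary source is the re-operation form: "The date of re-operation is recorded on the re-operation form", and "If the time to re-operation is ≤ 7 days then the patient will be classified as reoperation within 7 days = Yes".

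The need for a redo is also asked elsewhere. "Castor operation data forms contain the question" about any post-operative need to redo, and visits 1 to 4 and the unplanned visit form ask a similar question. If one of these answers points to a redo but "there is no accompanying re-operation form then the following approach will be used":

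- A positive answer "on the index operation form or the form for visit 1 (24 hours) or visit 2 (4 days) is Yes, then re-operation = Yes".
- A positive answer on the unplanned visit form counts only "if the date of the unplanned visit is within 7 days of the date of the index procedure".
- Clinical review may establish that a redo took place within 7 days.
- Anything else is missing.

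Two other sections show what else the free-flap operation form holds. Section 2.1.3.3.2 takes the item "Flap survival at recipient site at discharge" from it. Section 2.1.5.1.4, on 30-day re-operation, says that Castor's "Free Flap Operation Visit: Operation Data Form, collects information on whether a donor site re-operation was required", together with its date and type.

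Section 2.4.4.2.4 reports the endpoint as a proportion of procedures with 95% confidence limits and fits Model 4/4a, by surgery type and by prospective or retrospective subpopulation.

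**The concern.** The first fallback bullet treats three forms as equivalent evidence of timing. Visit 1 (24 hours) and visit 2 (4 days) are scheduled before day 7, so a 'Yes' there dates the event well enough. The operation form has no such anchor. The question on it concerns a post-operative event and, as quoted, sets no time limit. The free-flap version is evidently not closed on the day of surgery, since it carries status at discharge and a dated donor-site re-operation. A 'Yes' there shows that a redo occurred, not that it occurred by day 7.

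The rule also departs from the logic beside it. The unplanned visit form must pass a 7-day date check, and other undatable cases go to missing. Only the operation form is exempt. Clinical review is described solely as a route to 'Yes', so no step can reverse a wrong one.

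At stake is a secondary endpoint defined by a 7-day window. Follow-up runs to 30 days for flaps and replantations and to 24 weeks for lymphatic surgery, so there is time for later redos to be recorded. All retrospective data go into Castor (section 1.4), and section 2.5.6 expects a fair amount of missing retrospective data. The error may therefore differ between the two subpopulations that the SAP reports separately.

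**Working it through.** The documents give no expected 7-day redo rate, no late redo rate and no frequency of missing re-operation forms. There is no plan figure to reproduce. The check is first by logic, then by a simple formula with assumed inputs.

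**1. The rule applied to cases with no re-operation form**

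| Operation form | Visits 1, 2, 3 | Visit 4 | SAP result |
|---|---|---|---|
| No | all No | Yes | missing, unless review finds a redo within 7 days |
| Yes | all No | Yes | Yes within 7 days |

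The second row adds one undated answer to the first. That answer says nothing about timing, yet the result moves from missing to 'Yes', although three visits out to day 14 report no redo.

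**2. Formula**

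Let *t* be the true 7-day redo rate, *l* the rate of redos after day 7, and *u* the share of redos known only from an undated operation-form 'Yes'. Early undated redos are scored 'Yes' correctly. Late undated redos are scored 'Yes' wrongly. Leaving the other fallback routes aside:

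Reported rate = *t* + *l* × *u*, so the excess is *l* × *u*. It is never negative, and it is zero when *u* = 0.

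**3. Illustration with a proxy total**

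Total redo rate 10.7%: this is the flap registry's overall re-operation rate quoted in SAP section 2.4.6.2.4. It is not an anastomosis redo rate and serves only as a proxy. The late share (20-40%) and the share of late redos with no form but an operation-form 'Yes' (10-30%) are assumptions.

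- Late share 20%: *t* = 10.7 × 0.8 = 8.56%. Excess = 10.7 × 0.2 × 0.1 = 0.21, or 10.7 × 0.2 × 0.3 = 0.64 points. Reported 8.77% to 9.20%.
- Late share 40%: *t* = 10.7 × 0.6 = 6.42%. Excess = 10.7 × 0.4 × 0.1 = 0.43, or 10.7 × 0.4 × 0.3 = 1.28 points. Reported 6.85% to 7.70%.

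In relative terms this is 0.21/8.56 = 2.5% to 1.28/6.42 = 20%.

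**4. Wider assumed range**

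With *t* 3-8%, *l* 1-4% and *u* 10-50%, the excess runs from 1 × 0.1 = 0.1 to 4 × 0.5 = 2.0 points. The relative excess runs from 0.1/8 = about 1% to 2.0/3 = 67%.

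**5. What happens if undated cases are simply set to missing**

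Take *t* = 5%, *l* = 2%, *u* = 25%, with *u* the same for early and late redos. The undated cases are 5 × 0.25 = 1.25% (early) and 2 × 0.25 = 0.5% (late).

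- Current rule: 5 + 0.5 = 5.5%.
- All undated set to missing: (5 − 1.25)/(100 − 1.75) = 3.75/98.25 = 3.8%.
- All undated counted 'No': 3.75%. All counted 'Yes': 5.5%.

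Here, setting to missing misses the true 5% by more than the current rule does, and in the device's favour. The No/Yes pair brackets it.

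**The case against.** **It is only a fallback.** The SAP expects a re-operation form whenever a redo is reported, and the dated form is the primary source. The error needs a redo after day 7, no form, and a 'Yes' on the operation form, all together. This stands: the documents show that the rule can inflate the rate, not that it will.

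**The net direction is open.** A redo on days 5 to 7 that is first reported at visit 3, with no form and no operation-form 'Yes', becomes missing unless review dates it. That pulls the rate down. A reader might infer that the reported 7-day rate will be too high overall. The documents do not support that; only the effect of this one rule has a certain sign.

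**The case report form is not available.** Its heading or instructions might limit the question to 7 days, as the endpoint is worded for flaps and replantations in the protocol synopsis. This cannot be excluded, though the lymphatic item in the same synopsis has no 7-day limit.

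**The form evidence is uneven.** Later outcomes are shown for the Castor free-flap form and Dendrite form H. For the Castor replantation and lymphatic operation forms there is only the wording of the question. One might infer that lymphatic redos up to 24 weeks enter the rate, or that retrospective forms are all completed after follow-up ends. Both are plausible, but neither is stated.

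**The rule may be deliberately conservative.** Counting an undated complication against the device is defensible in a single-arm study. But the SAP does not give that reason, and the date check and missing default in the same list do not follow it.

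**No decision depends on it.** The endpoint is secondary, with no threshold or comparator. With an assumed 402 procedures, the 95% half-width near 8.6% is 1.96 × √(0.086 × 0.914/402) = 2.7 points, larger than the illustrated excess. This stands and limits the importance of the point.

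**Conclusion.** The point holds as a defect in a stated rule: followed as written, section 2.1.3.2.4 can score a redo after day 7 as a 7-day redo, even against 'No' at visits 1, 2 and 3. The error from this rule can only be upward. Its size is unknown: zero with complete re-operation forms, 0.2 to 1.3 points under the proxy assumptions, and up to 2.0 points at the edge of the wider assumed range. It may differ between prospective and retrospective patients, but the documents do not show that it will. The support is firm for the free-flap form and thinner for replantation and lymphatic surgery. The net bias of the whole derivation is uncertain. This is a minor correction, worth making because it costs little.

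**What to change.** Remove the index operation form from the first fallback bullet and treat a 'Yes' there as a redo of unknown date. Then, in order:

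1. Use any re-operation date recorded on other forms (sections 2.1.2 and 2.1.5.1.4), where the recorded type of re-operation shows that it is the redo in question.
2. Otherwise use the visit answers. 'Yes' at visit 1 or 2 gives within 7 days = Yes. 'No' at visits 1, 2 and 3 with the first 'Yes' at visit 4 gives within 7 days = No.
3. Send the rest, such as a first 'Yes' at visit 3 or missing visit forms, to the existing clinical review, and state that it may conclude Yes or No.
4. For cases still undated, report the 7-day rate twice: all counted 'Yes' (the current rule) and all counted 'No'. State their number by subpopulation and surgery type. Do not rely on setting them to missing alone, since that can silently lower the rate.

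The cost is a change of SAP wording, a little more derivation work and one sensitivity table. No new data are needed.
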